The screening period extends from 3 months before surgery to 12 months after breast cancer surgery. Patients who agree to participate are scheduled for a screening visit between 3 and 12 months post-surgery. If they present with ICBN, defined by a DN4 score ≥ 4 , they will be included and randomized to receive either pregabalin (standard treatment) or topical capsaicin patch (experimental treatment), both of which are indicated for the management of peripheral neuropathic pain.

Pregabalin will be initiated with a gradual titration to reach a dose of 600 mg/day in two divided doses, depending on patient tolerability.

Capsaicin patches will be applied in a hospital setting to the painful area for 1 hour, with applications scheduled every 90 days.

All patients will undergo assessments at T0 (± 7 days) and T6 (± 7 days) regarding pain evolution (intensity and area), treatment tolerability, and quality of life.

The end of treatment and study follow-up is planned at the final pain-evaluation visit (T6).

F) STATISTICAL CONSIDERATIONS

SAMPLE SIZE DETERMINATION	
Statistical analyses will be performed using R software.
 
A total of 772 patients will be included, allocated into two balanced groups.
 
Sample size calculation
 
An interim analysis is planned once 300 patients have been included (minimum 150 per arm), based on the primary endpoint.
 
Alpha allocation:
 
 - 0.005 for the interim analysis - 0.045 for the final analysis 
Assumptions for calculating the required sample size:
 
 - At baseline, the standard deviation of NRS pain score is estimated at 2.0. - The expected mean difference in NRS (Capsaicin – Pregabalin) is 0. - The non-inferiority margin is set at +0.4 points on the NRS. - One-sided alpha risk: 4.5%. - Statistical power: 80%. 
Under these assumptions, 322 patients per arm are required (644 total). Considering a 20% rate of non-evaluable patients at 6 months, the total required sample size is 772 patients (386 per arm).

----------------------------------	---

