------------------------------	---

	
 - baseline NRS pain score, - treatment arm. 
Statistical stopping rules
 
An interim analysis will be conducted after inclusion of 150 patients per arm based on the primary endpoint (NRS at T6).
 
If a statistically significant difference in efficacy is observed at $\alpha = 0.005$, the study will be stopped for efficacy, regardless of which treatment demonstrates superiority.
 
Handling of missing, unused, or invalid data
 
Missing data for the numerical pain scale (NRS), painful area, and PGIC will not be imputed.
 
The proportion of missing data will be compared between arms using a Chi-square test.
 
Baseline characteristics of patients with missing data will also be compared.
 
Missing data for quality-of-life questionnaires (QLQ-C30, QLQ-BR23, EQ-5D) may be imputed according to EORTC manual recommendations.
 
Management of amendments to the analysis plan
 
Modifications to the statistical analysis plan may be proposed by the data monitoring committee (interim analysis, statistical tests, adverse event review, secondary objectives) if justified by emerging literature.
 
Protocol deviations will be identified and quantified.
 
Randomisation
 
Patients with a positive DN4 score will be randomized directly through the eCRF to be allocated to one of the following treatment arms:
 
 - Arm A (experimental): CAPSAICIN (patch), application of capsaicin patches to the painful area for 1 hour, with applications repeated every 3 months. - Arm B (standard): PREGABALIN (oral), oral pregabalin with progressive dose escalation. 
Validation of the randomization will automatically generate a confirmation email specifying the treatment arm allocated to the patient.
 
Randomization will be performed using balanced block allocation, stratified according to the following factors:
 
 - Study center - Pain intensity on the numerical rating scale (≥ 5) - Age (≥ 65 years) - HADS score (Incomplete, ≤ 18, > 18) - Pain duration (< 3 months or ≥ 3 months)
--	---

G) STUDY CALENDAR

DURATION OF INCLUSION PERIOD	36 months
TREATMENT DURATION	6 months
POST TREATMENT FOLLOW UP	6 months
STUDY COMPLETION DURATION (INCLUDING FU PERIOD)	42 months

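### The 0.005 deducted from the non-inferiority level for the interim look protects almost nothing as the look is described; recovering it is a small, free gain in power, not the repair of an error

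*Combined protocol and SAP*

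**What the plan says.** Section F, Sample size determination, allocates "0.005 for the interim analysis" and "0.045 for the final analysis". It names no overall level, no spending function and no information fraction; the 5% total is simply the sum of the two. The sample size rests on "One-sided alpha risk: 4.5" per cent and "Statistical power: 80" per cent, with an SD of 2.0, a margin of 0.4 and a true difference of zero. This gives 322 evaluable patients per arm, raised to 386 per arm (772 in total).

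On timing, the same section says: "An interim analysis is planned once 300 patients have been included (minimum 150 per arm), based on the primary endpoint".

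Section F, Statistical stopping rules, describes what the look does. On a significant difference at 0.005, "the study will be stopped for efficacy, regardless of which treatment demonstrates superiority". No interim non-inferiority claim is described, and sidedness is not given. This paragraph labels the primary endpoint as the NRS at T6, whereas section C, Primary Objective and Endpoint, defines it as the change from T0 to T2.

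**The concern.** A level is deducted from a final test to pay for the chance of a false claim of the same kind at an earlier look. Here the final claim is non-inferiority and the interim claim, as written, is superiority of one arm. When capsaicin is truly worse by the full margin, a look that must show capsaicin significantly better will almost never do so. The 0.005 deducted from the non-inferiority test therefore pays for a risk that hardly exists.

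Even if the interim did test non-inferiority, adding the two levels ignores that interim patients are also in the final analysis, so the chance of crossing at least one boundary is below the sum.

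At stake is a little power in a trial with no reserve: 322 evaluable per arm gives 80.0%, and the plan's own 20% non-evaluable rate applied to 386 leaves about 309.

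**Working it through.** **Inputs (section F, Sample size determination).** SD: "the standard deviation of NRS pain score is estimated at 2.0". Margin Δ: "The non-inferiority margin is set at +0.4 points on the NRS". True difference 0, equal arms, power 80%, levels 0.005 and 0.045, interim at 300 included.

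**1. The plan's own figure.** n per arm = 2 × SD² × (z₁₋α + z₀.₈₀)² / Δ².
- At 0.045: 8 × (1.6954 + 0.8416)² / 0.16 = 321.8, so 322. The plan's number reproduces.
- At 0.05: 8 × (1.6449 + 0.8416)² / 0.16 = 309.1, so 310.

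**2. Interim as a superiority look, same visit.** Suppose capsaicin is truly 0.4 worse. A two-sided 0.005 look favours capsaicin with probability Φ(−2.807 − 0.4/SE), where SE = √(8/n).
- 150 per arm: SE = 0.2309; Φ(−2.807 − 1.732) = Φ(−4.539) = 2.8 in a million.
- 120 per arm (20% not evaluable): SE = 0.2582; Φ(−2.807 − 1.549) = Φ(−4.356) = 6.6 in a million.

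If 0.005 applies to one direction, the figures are 8 and 19 in a million. Adding 0.000007 to 0.045 bounds the total non-inferiority error at about 4.5%. With a final level of 0.05, the same addition gives at most 0.050007. The joint calculation, counting the stops that favour pregabalin, gives slightly under 5% (4.995% to 4.997% with 322 per arm at the end).

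**3. Power.** Power = Φ(0.4/√(8/n) − z₁₋α).

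| Evaluable per arm | at 0.045 | at 0.05 |
|---|---|---|
| 322 | Φ(2.538 − 1.695) = 80.0% | Φ(2.538 − 1.645) = 81.4% |
| 309 (386 × 0.8 = 308.8) | Φ(2.486 − 1.695) = 78.5% | Φ(2.486 − 1.645) = 80.0% |

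**4. Interim as a one-sided 0.005 non-inferiority look, same visit.** The two statistics are bivariate normal with correlation √t, where t is the information fraction. Total error = 0.005 + 0.045 − P(both crossed).

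| t | √t | Total error | Final level for 5% | Power at 322 |
|---|---|---|---|---|
| 240/644 = 0.373 | 0.610 | 4.73% | 0.0477 | 80.8% |
| 300/772 = 0.389 | 0.623 | 4.72% | 0.0478 | 80.8% |
| 300/644 = 0.466 | 0.683 | 4.68% | 0.0483 | 81.0% |

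**5. Non-inferiority look at T6, final test at T2.** The correlation becomes √t times the within-patient T2–T6 correlation, which the documents do not give. Assumed values, at t = 0.389:

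| Assumed correlation | Error with 0.045 | Final level for 5% | Error with 0.0478 |
|---|---|---|---|
| 0.7 | 4.84% | 0.0466 | 5.12% |
| 0.5 | 4.90% | 0.0460 | 5.17% |
| 0.3 | 4.94% | 0.0456 | 5.22% |

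**The case against.** The strongest reply is that nothing is broken. An additive (Bonferroni-type) split is valid at any information fraction and any correlation. The sample size was computed at the same 4.5%, so 322 evaluable patients per arm do deliver the planned 80%. The 5% benchmark appears nowhere as such. While the interim's hypothesis, sidedness, visit and counted population are unsettled (300 are included rather than evaluable, and section F places the non-inferiority test in the per-protocol population), the additive split is the choice that stays safe. The gain is also small. All of this stands, and it is why the point is an efficiency gain and not an error.

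It does not remove the point. For the superiority look that the stopping rules describe, the deduction from non-inferiority has almost nothing to protect, and dropping it costs only wording once the interim is settled.

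A reader might infer that the stated boundaries use about 4.7% of the 5%. That figure needs an interim non-inferiority test at the same visit, which the stopping rules do not describe. A reader might also infer that a final level of 0.0478 is safe whatever the interim tests. Step 5 shows that it is not when the visits differ.

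**Conclusion.** The point holds as a minor, cost-free improvement. With the interim as a superiority look at the same visit as the final test, non-inferiority is in effect tested once, at about 4.5%. Testing it at 0.05 gains 1.4 points of power at 322 per arm (80.0% to 81.4%) and 1.5 at 309 (78.5% to 80.0%). With a same-visit non-inferiority interim, the gain is about 0.8 to 0.9 points at 322.

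This rests on an SD of 2.0, normal statistics, a true difference of zero for power, and a 5% total read from the sum. The figure of 3 to 7 in a million also needs the interim and final tests to use the same visit.

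It would be too strong to say that planned power is lost through the split: the 80% target is met at 322. The 78.5% at 309 comes from a separate matter, namely that 386 is 322 × 1.2 (386.4), whereas allowing for 20% loss needs 322/0.8 = 403. That shortfall needs its own correction.

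**What to change.** 1. Reconcile sections C and F on the interim: which hypothesis, one- or two-sided, and which visit (T2 or T6).
2. If it stays a superiority look on the primary endpoint, test non-inferiority once at one-sided 0.05 and apply the 0.005/0.045 split only to the superiority test.
3. If it becomes a one-sided 0.005 non-inferiority look at the same visit, derive the final level from the joint distribution at the information fraction actually reached, for example with a spending function that spends 0.005 at the interim. Expect about 0.0477 to 0.0483 for information of 0.37 to 0.47.
4. If the interim and final visits differ, do not use 0.0478. Keep 0.045, or a level that allows for the lower correlation.
5. Keep 772 patients, state the overall level explicitly, and restate the final level and the resulting power.

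The cost is SAP wording and, under item 3, one boundary calculation, settled before any comparative data are seen. No patients or data are added.

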DESCRIPTION OF ANALYSIS SETS	
Description of planned statistical methods
 
A descriptive analysis of the study sample will be performed. Data will be presented as follows:
 
 • Qualitative variables: expressed as percentages. • Quantitative variables: expressed as mean and standard deviation, or median and range, depending on the distribution. 
Comparisons will be performed as follows:
 
 • Qualitative variables: using the Chi-square test or Fisher's exact test when appropriate. 
Quantitative variables: using Student's t-test or a non-parametric test (Wilcoxon test) depending on distribution and normality assumptions.
 
Definition of Analysis Populations
 
 • The ITT population includes all randomized patients in the CAPTRANE study. Patients are analyzed according to the treatment arm to which they were randomized, regardless of the treatment actually received. • Modified Intention-to-Treat Population (mITT) • The mITT population includes all randomized patients who received at least one administration of study treatment; i.e., excluding patients withdrawn prematurely or incorrectly included before receiving treatment. Patients are analyzed according to their allocated arm, regardless of treatment actually received. • Per-Protocol Population (PP) • The PP population includes all randomized patients who received the allocated treatment according to the protocol. Patients who received any treatment other than that assigned are excluded from the analysis. • If non-inferiority is demonstrated at the pre-specified 0.4 threshold (primary endpoint in the PP population), a Student's t-test will be used to compare the mean 24-hour maximum NRS pain scores at T2 (2 months after randomization) between the capsaicin and pregabalin arms, in the mITT population. • Mean 24-hour NRS scores at T6 will be compared between arms using a Student's t-test. • The percentage of patients with at least a "notable improvement" (PGIC score ≥ 5) will be compared between arms using a Chi-square test. • Reduction in painful area will be expressed as a percentage relative to baseline. • Differences in painful area between T2–T0 and T6–T2 will be compared using a Student's t-test. • All grade ≥ 2 adverse events will be described by category and by treatment arm. • The number of patients experiencing at least one grade ≥ 2 toxicity event will be compared using a Chi-square test. • The percentage of patients with $\geq 5\%$ weight gain will be compared between arms using a Chi-square test. • A subgroup analysis of NRS pain scores at T2 and T6 will be performed among patients with probable anxiety disorder and those with probable depressive disorder according to baseline HADS scores. • A multivariable linear regression model will be used to estimate the impact of pain duration before inclusion (expressed in months) on pain intensity at T2 and T6 (NRS), adjusted for:

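### The 20% allowance multiplies 644 by 1.2 instead of dividing by 0.8, so if 20% are non-evaluable for the primary analysis, 772 patients give 78.5% power, not 80%

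*Combined protocol and SAP*

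**What the plan says.** The assumptions are listed in section F, sample size determination:

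- Spread of the scores: "At baseline, the standard deviation of NRS pain score is estimated at 2.0"
- True effect: the two arms are assumed to be equal on average
- Margin for the test: "The non-inferiority margin is set at +0.4 points on the NRS"
- Level of the final test: 4.5%, one-sided
- Target power: 80%

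From these the plan concludes: "Under these assumptions, 322 patients per arm are required (644 total"). It then inflates: "Considering a 20% rate of non-evaluable patients at 6 months, the total required sample size is 772 patients (386 per arm").

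Three other places bear on what the allowance has to cover.

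- **Time point.** Section C (primary objective and endpoint) measures the change in pain score from randomisation to month 2. The statistical stopping rules in section F identify the primary endpoint as the pain score at month 6.
- **Population.** The description of analysis sets in section F places the non-inferiority test in the per-protocol set: "If non-inferiority is demonstrated at the pre-specified 0.4 threshold (primary endpoint in the PP population").
- **Missing data.** Section F says that missing pain scores are not imputed.

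**The concern.** A rate of non-evaluable patients is a share of those enrolled. To finish with 644 evaluable patients, the enrolled number must be 644 divided by the evaluable share, 0.8. The plan adds 20% of 644 instead, which gives a smaller number. Since missing pain scores are not imputed, a patient without one drops out of the primary comparison, and nothing else in the plan makes up the difference. The two consecutive sentences that give 644 and 772 therefore do not agree with each other under the plan's own rate.

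The allowance is also not clearly tied to the primary analysis. It is stated at 6 months, the primary time point differs between sections, and the term non-evaluable is not defined for a per-protocol test. At stake is whether the stated 80% power is what 772 patients provide. The type I error, the margin and the test are not affected.

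**Working it through.** **Inputs**, all from section F, sample size determination: SD 2.0, true difference 0, margin 0.4, one-sided alpha 0.045 (z = 1.6954), power 80% (z = 0.8416), equal arms.

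**1. Reproduce the evaluable number.**

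n per arm = 2 × (1.6954 + 0.8416)² × 2.0² / 0.4² = 321.8, rounded up to 322, so 644 in total. This matches the plan. A t-based calculation gives 323. Other alphas do not fit: 0.05 gives 310 and 0.025 gives 393.

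**2. Reproduce the inflated number.**

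- 644 × 1.2 = 772.8 and 322 × 1.2 = 386.4. Rounded down, these are the stated 772 and 386.
- 644 / (1 − 0.20) = 805. Per arm, 322 / 0.8 = 402.5, so 403 per arm and 806 in total.
- The stated figure is 805 − 772 = 33 short (33 / 772 = 4.3%), or 34 short with equal arms.

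**3. What 772 delivers if 20% are non-evaluable for the primary analysis.**

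- Evaluable: 772 × 0.8 = 617.6, or 308.8 per arm. This is 644 − 617.6 = 26.4 fewer than required.
- Power = Φ(0.4 / (2.0 × √(2 / 308.8)) − 1.6954) = 78.5% (78.4% t-based).
- With 403 per arm and the same loss, 322.4 per arm remain and power is 80.1%.

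**4. The rate at which 772 is enough.**

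1 − 644 / 772 = 0.166, so 80% power holds up to 16.6% non-evaluable.

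**5. Power of 772 over a range of rates.** The documents give no rate for month 2 or for the per-protocol set, so these rates are assumptions.

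| Non-evaluable for the primary analysis | Evaluable per arm | Power |
|---|---|---|
| 5% | 366.7 | 84.4% |
| 10% | 347.4 | 82.7% |
| 15% | 328.1 | 80.7% |
| 16.6% | 321.9 | 80.0% |
| 20% | 308.8 | 78.5% |
| 25% | 289.5 | 76.1% |

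**The case against.** The strongest reply is that the consequence is small. A loss of 1.5 points of power is what an SD of 2.04 instead of 2.0 would cause (2.0 × √(322 / 308.8) = 2.04), and the plan gives the SD only as an estimate. This stands, and it sets the grade: the point is minor.

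A second reply is that the shortfall is not certain. If the primary analysis is at month 2, cumulative drop-out by then cannot exceed drop-out by month 6, and 772 is enough up to 16.6%. This also stands. Exclusions from the per-protocol set could push the other way, so the net rate at month 2 is unknown.

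Three stronger readings are tempting, and the documents do not support them.

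- A reader might infer that month 6 is simply the wrong time point for the allowance. Section C supports month 2, as does the follow-on superiority test in section F. The stopping rules name month 6, however, and the 6-month allowance agrees with them. The defect is an unresolved contradiction.
- A reader might infer that the rate refers to the wrong population. The plan does not define non-evaluable, and the 20% may already include per-protocol exclusions. It is undefined, which is a lesser fault.
- A reader might infer that adjusting the analysis for baseline pain would make up the loss. That depends on the correlation between baseline and follow-up scores, which the documents do not give.

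None of this rescues the arithmetic. No other section corrects the 772, and no reserve is described.

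**Conclusion.** The inflation is wrong as written. Under the plan's own 20%, 772 patients leave about 618 evaluable instead of 644, and power is 78.5% instead of 80%. This assumes that the 20% applies to the primary analysis and that the SD, margin, true difference and alpha are as stated. If month 6 is the primary time point and non-evaluable covers every exclusion from the per-protocol set, the shortfall follows directly. If month 2 is the primary time point, the plan gives no rate for its primary analysis, and power is above or below 80% according to whether that rate is below or above 16.6%.

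A reader might infer that the trial is seriously underpowered. The figures do not show that: across assumed rates of 10% to 25%, power runs from 82.7% to 76.1%. This is a minor correction to a central design statement.

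**What to change.** Keep 772 and change the wording in section F:

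1. State that 772 patients with 20% non-evaluable give about 309 evaluable per arm and 78.5% power, and that 80% power holds up to 16.6% non-evaluable.
2. Reconcile the primary time point between section C (month 2), the sample size paragraph (allowance at 6 months) and the stopping rules (month 6).
3. Define the allowance as the share of randomised patients not evaluable for the primary endpoint in the per-protocol set at the reconciled time point, covering both missing scores and protocol exclusions. Do not carry the 20% over to that definition without a reason.
4. Show power at assumed rates of 10% (82.7%), 15% (80.7%), 20% (78.5%) and 25% (76.1%).

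The cost is wording only, with no added patients. The downside is a slightly less favourable power statement. Raising enrolment to 806 would restore 80% at a 20% loss, but a gap of 1.5 points does not call for it.

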PROTOCOL CAPTRANE

Multicenter, open-label, randomized study comparing topical treatment with 8% capsaicin patch (Qutenza) to oral pregabalin in the early management of intercostobrachial neuralgia (ICBN) following primary surgery for breast cancer.

A) CLINICAL TRIAL IDENTIFICATION

STUDY TITLE	Multicenter, open-label, randomized study comparing topical treatment with 8% capsaicin patch (Qutenza) to oral pregabalin in the early management of intercostobrachial neuralgia (ICBN) following primary surgery for breast cancer.
SHORT TITLE	CAPTRANE
INVESTIGATOR COORDINATOR	[name]
EUDRACT	2018-003559-39
REF ANSM	MEDAECNAT-2018-20-00041
ETHICS COMMITTEE NAME	CPP SUD MEDITERRANEE IV (MONTPELLIER)
REF ETHICS COMMITTEE	18.11.04
N° CLINICAL TRIAL.GOV	NCT03794388

B) STUDY BACKGROUND

Epidemiology of Breast Cancer

Breast cancer is the most common cancer in women in both the European Union and the United States. In France, 54,000 new cases of breast cancer in women were recorded in 2015. Although its incidence has been decreasing over the past decade, breast cancer remains the most frequent malignancy, ahead of colorectal and lung cancer (2). This cancer is far less common in men.

Breast cancer mortality has been declining since the late 1990s. According to data from the French National Cancer Institute, the five- and ten-year net survival rates are high, at 86% and 76% respectively for individuals diagnosed between 1989 and 2004 (2). Breast cancer has therefore become a chronic disease, and patients must learn to live with it as well as with the adverse effects linked either to the disease itself or to the treatments administered.

As highlighted by the third Cancer Plan (Action 8.3: "Improve the management of physical sequelae of cancer treatments") (3), in continuity with the previous Cancer Plan and the fourth National Pain Management Plan (4), pain is a major criterion impacting the quality of life of patients treated for breast cancer.

Neuropathic Pain in Patients with Breast Cancer

Definitions

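### The conditional superiority test at 2 months leaves out randomised patients who never start treatment, in an open-label trial where starting can depend on the arm

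*Combined protocol and SAP*

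**What the plan says.** Section F, Definition of Analysis Populations, sets out three populations.

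- ITT: "The ITT population includes all randomized patients in the CAPTRANE study", analysed in the arm allocated.
- mITT: "The mITT population includes all randomized patients who received at least one administration of study treatment", with the explanatory clause "excluding patients withdrawn prematurely or incorrectly included before receiving treatment". These patients too are analysed in the allocated arm, whatever they actually received.
- Per-protocol (PP): patients who received the allocated treatment according to the protocol.

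Non-inferiority is judged in PP. If it is shown, a t-test compares the mean T2 scores "between the capsaicin and pregabalin arms, in the mITT population". No analysis names the ITT set, and no ITT sensitivity analysis of the superiority test is described.

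Three other places bear on this:

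- The title describes a "Multicenter, open-label, randomized study comparing topical treatment with 8% capsaicin patch".
- Section F, Randomisation: "Validation of the randomization will automatically generate a confirmation email specifying the treatment arm allocated to the patient".
- Section F, on missing data: "Missing data for the numerical pain scale (NRS), painful area, and PGIC will not be imputed".

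The treatment table and therapeutic schema in section E show that capsaicin is applied in hospital for one hour, while pregabalin is an oral capsule.

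**The concern.** Leaving never-treated patients out of an efficacy comparison is usually harmless when the decision to start cannot depend on the allocated arm, as under effective blinding. Here patient and site know the arm before the first administration, and the two arms ask for different things at that point: a hospital attendance or a capsule. Patients who do not start may therefore differ between arms in number, in prognosis, or in both. Membership of the mITT set is settled after the arm is known, so randomisation no longer guarantees that the two sets are comparable.

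The objective is stated for an early management strategy. A patient who learns the allocation and never starts is part of how that strategy performs. Superiority is the strongest claim the trial could make, and the test has no margin to absorb a small bias. Depending on which arm loses more patients, the bias could create a difference or hide one.

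**Working it through.** **The plan's own figure.** Section F gives SD 2.0, margin 0.4, expected difference 0, one-sided alpha 4.5% and power 80%.

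n per arm = 2 × 2.0² × (1.695 + 0.842)² / 0.4² = 321.8, so 322, or 644 in total. This matches the plan. The stated total of 772 (386 per arm) corresponds to 644 × 1.2 = 772.8. The point disputes neither number.

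**Who is lost.** The clause on withdrawn or incorrectly included patients explains the at-least-one-administration rule and is limited to the time before treatment. The patients lost from mITT are therefore those never treated.

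**Inputs for the illustration**

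- SD 2.0, from section F.
- 309 per arm: 386 × 0.80 = 308.8. This is an assumption, because the plan states its 20% non-evaluable rate at 6 months and the test is at 2 months.
- Two-sided alpha 0.045. The plan gives 0.045 to the final analysis and one-sided 4.5% to the non-inferiority calculation, but states neither alpha nor sidedness for the superiority test. This is an assumption.
- Non-start fractions fC (capsaicin) and fP (pregabalin), and the offset d by which non-starters' mean T2 score exceeds that of starters. The documents give none of these; all are assumptions.

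**Formulas.** Each arm's full mean equals its starters' mean plus f × d. If the randomised arms do not differ, the mITT difference (capsaicin minus pregabalin) is

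shift = −(fC − fP) × d.

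SE = 2.0 × √(2/309) = 0.161, and the critical value for two-sided 0.045 is 2.005.

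Total two-sided error = Φ(−2.005 + |shift|/SE) + Φ(−2.005 − |shift|/SE).

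**Results**

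| fC vs fP | d (points) | Shift | Shift/SE (absolute) | Two tails | Total error |
|---|---|---|---|---|---|
| equal | equal | 0 | 0 | 2.25% + 2.25% | 4.5% |
| 5% vs 2% | 1.0 | −0.03 | 0.186 | 3.45% + 1.42% | 4.9% |
| 5% vs 2% | 1.5 | −0.045 | 0.280 | 4.23% + 1.12% | 5.3% |
| 10% vs 2% | 1.0 | −0.08 | 0.497 | 6.58% + 0.62% | 7.2% |

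With more non-starters on pregabalin the sign of the shift reverses.

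**Dependence on the unstated alpha.** At two-sided 5% the last three totals are 5.4%, 5.9% and 7.9%. Counting only false superiority of capsaicin, a one-sided 2.5% test gives 3.8%, 4.6% and 7.2%, and a one-sided 4.5% test gives 6.6%, 7.8% and 11.5%. The direction is the same throughout; the size depends on a choice that the plan does not record.

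**Does naming ITT suffice?** No. NRS is not imputed, so a t-test labelled ITT uses only patients with a T2 score. If no never-treated patient has one, the ITT and mITT tests use the same patients.

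**The case against.** The strongest case against is that this is a mild form of mITT. It drops only never-treated patients and keeps everyone else in the allocated arm. A reader might infer that it also removes patients found ineligible at any time after the arm is disclosed. The wording does not support that: an ineligible patient who received treatment stays in. This limit stands.

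Differential non-start is not shown either. The documents give no non-start rate and no interval between randomisation and first administration, so non-starters may be few. The non-inclusion criteria remove some arm-specific reasons for not starting, because they bar hypersensitivity to either drug and inability to comply with follow-up. A difference is plausible from the two modes of starting, and no more than that.

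A reader might also say that the false-positive rate nearly doubles, from 2.5% to 4.6%. That figure assumes a one-sided 2.5% test, which the plan does not state, and counts one tail only. In the same scenario, total two-sided error at 4.5% rises by less than one percentage point.

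The plan does compare the proportion of missing data between arms, together with the baseline characteristics of patients with missing data. It does not say in which population, and such a comparison could reveal an imbalance but would not correct it.

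Finally, superiority is a conditional secondary objective with an expected difference of 0. That limits the stakes but leaves the choice of analysis set unexplained.

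**Conclusion.** The point holds in a limited form. The conditional T2 superiority test uses a set settled after the arm is known, in an open-label trial whose arms start treatment differently, while the ITT set that would avoid this is defined and assigned to no analysis. Nothing in the documents cures it.

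The size of any bias is unknown. Under the assumed rates it runs from nil (equal non-start rate and prognosis) through 0.03 to 0.045 points (total error 4.9% to 5.3% against 4.5%) to 0.08 points (7.2%). These figures rest on SD 2.0, 309 per arm, a two-sided 4.5% test, and assumed non-start rates and offsets.

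The documents do not support a conclusion that the result will be biased, or that it will favour capsaicin. Nor does this point reach the primary non-inferiority conclusion, which is judged in PP under a different rule. The change is worth making because it is cheap and removes a dependence that the plan neither prevents nor checks.

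**What to change.** 1. In section F, name the ITT population for the T2 superiority test and keep mITT as a supportive analysis. The ITT definition needs no change.
2. Seek the T2 NRS from randomised patients who never start treatment, where they consent to give it.
3. Because NRS is not imputed, add a pre-specified sensitivity analysis for randomised patients who still lack a T2 score. Without it the ITT test drops them as well.

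The planned total of 772 does not change. The costs are a change of SAP wording, modest effort to follow patients who did not start, some of whom will be hard to reach, and slight dilution of a true difference when non-starters are included.
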